### **3 HANDLING OF MISSING DATA AND STUDY BIAS**

Appropriate methods to deal with missing values will be chosen after exploring the data. Patients with missing outcomes and patients without missing outcomes will be compared to determine the type of missingness (missing at random/missing completely at random/missing not at random). Knowledge from researchers who implement the study will also be considered to determine type of missingness. Based on type and amount of missingness, deletion and/or imputation might be applied.

### **4 STATISTICAL ANALYSIS OF THE PRIMARY AND SECONDARY STUDY OBJECTIVES**

#### **4.1 Analysis of the Primary Study Objective**

##### Primary Outcome:

The primary analysis will include all subjects meeting inclusion and exclusion criteria and who have completed a year of treatment/placebo and the 3 month post-treatment assessment. EDSS Plus composite score from 3 month post-treatment assessment will be compared to baseline.

Descriptive statistics will be calculated for patients at baseline for the entire cohort as well as by treatment status. Treatment and placebo group patients will be compared on continuous and discrete baseline characteristics to assess randomization.

The EDSS-Plus scale will be used as our primary endpoint with improvement on one or more of the 3 components (EDSS, T25FW and 9HPT). Improvement is defined as  $\geq 1$  point decrease from baseline EDSS if EDSS at entry is  $\leq 5.5$ , and a  $\geq 0.5$  point decrease from baseline EDSS if EDSS at entry is  $\geq 6.0$ ,  $\geq 20\%$  positive change in T25FW, and/or  $\geq 20\%$  positive change in 9HPT confirmed. The primary endpoint of improvement on one or more of the 3 EDSS-Plus categories between treatment and placebo groups will be assessed bi-varately using the chi-square or Fisher's exact test, as appropriate, at year 1, 2, and 3 of the study. Adjusted odds ratio (95%CI) between treatment and placebo groups at each time point will be estimated through mixed effect logistic regression with fixed effect of time, treatment, relevant covariates, and random effect of patients. The three components of the EDSS-Plus composite score will also be assessed individually at all time points. A longitudinal linear mixed-effect model will be used to assess longitudinal change (percentage change in mean time) from baseline to 3 years for T25FW and 9HPT, with random intercepts for patients and taking into account treatment status (treatment vs placebo), disease subtype (SPMS vs PPMS) and time-progression status interaction.

**Study Name:** Autologous, Bone Marrow-Derived Mesenchymal Stem Cell-Derived Neural Progenitor Cells, Expanded Ex Vivo; Administered Intrathecally (Phase II Trial)

**Principal Investigator:** [name]

Under parallel design, we will compare the outcomes of interest between the two study treatments, with outcomes at 1 year as the primary time point, secondary analyses will evaluate outcomes at years 2 and 3.

For comparisons via association tests, number (%) of events in the two groups and p-values from Chi-squared or Fisher's exact test will be reported. For regressions, odds ratios (95% CI) between the two groups and p-values from the mixed-effect model will be reported.

Appropriate method to deal with missing values will be chosen after exploring the data collected. Based on reason(s) and amount of missingness, deletion and/or imputation might be applied.

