## SAP Revision History

Version #	Version date	Reason for Revision
Version 1	Started Nov 2019 – Issued Dec 2020	Objective of SAP: To describe planned analysis of study objectives prior to data analysis (anticipated initial data analysis to be performed December 2021).
Version 2	July 2021	Finalize SAP for submission to FDA: update personnel list, update study design to indicate parallel group design, more detailed description of statistical analysis added.

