### 1.2 Study Design

The study is a Phase II, double-blind, placebo-controlled, randomized, parallel group design with a compassionate crossover element. The IT-MSC-NP treatments and all clinical assessments take place at a single center (Tisch MSRCNY). Both the patient and the examining neurologist are blinded to the treatment. The treating clinician ([name], principal investigator) and the cell manufacturing coordinator ([name], co-PI) are not blinded. The total study duration is 3 years upon enrollment. Each subject will initially attend 1 screening visit, 1 visit for bone marrow extraction, and 1 baseline visit. In the first year, each subject will receive 6 intrathecal injections of MSC-NPs or placebo spaced 2 months apart, followed by an outcome assessment visit 3 months after the 6th treatment. In the second year, subjects will cross-over into the opposite group, and will receive 6 intrathecal injections of placebo or MSC-NPs spaced 2 months apart, followed by an outcome assessment visit 3 months after the 12th treatment. There is an additional follow-up visit at the end of year 3.

**Study Name:** Autologous, Bone Marrow-Derived Mesenchymal Stem Cell-Derived Neural Progenitor Cells, Expanded Ex Vivo; Administered Intrathecally (Phase II Trial)

**Principal Investigator:** [name]

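### SAP 4.1 promises an adjusted odds ratio at every time point, but the logistic mixed model it lists can give only one common odds ratio, over visits that span the year 2 crossover

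*SAP*

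**What the plan says.** SAP 4.1 plans two kinds of between-group analysis for the primary endpoint, which is improvement on at least one EDSS-Plus component.

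- **Unadjusted:** chi-square or Fisher's exact test, "as appropriate, at year 1, 2, and 3 of the study".
- **Adjusted:** the stated target is "Adjusted odds ratio (95%CI) between treatment and placebo groups at each time point". On how to obtain it, the SAP says that it "will be estimated through mixed effect logistic regression with fixed effect of time, treatment, relevant covariates, and random effect of patients".

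The section then sets the priority of the visits: "with outcomes at 1 year as the primary time point, secondary analyses will evaluate outcomes at years 2 and 3". On reporting it says: "For regressions, odds ratios (95% CI) between the two groups and p-values from the mixed-effect model will be reported".

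For T25FW and 9HPT, SAP 4.1 adds a linear mixed model from baseline to 3 years, "taking into account treatment status (treatment vs placebo), disease subtype (SPMS vs PPMS) and time-progression status interaction". Protocol 9.3 shows that progression status means SPMS versus PPMS, so the only interaction listed is time by subtype.

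SAP 1.2 describes a "parallel group design with a compassionate crossover element", in which all subjects move to the opposite group in year 2. The SAP Revision History gives as one reason for version 2: "update study design to indicate parallel group design". Protocol 3 and the schedule in Protocol 6.4 move the treatment and placebo labels at crossover.

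**The concern.** The sentence that defines the adjusted analysis promises one odds ratio per visit from a model that contains only one. The SAP does not say which half governs.

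In a trial without crossover, a common odds ratio might be a tolerable summary. Here the comparison changes in year 2. Month 13 compares MSC-NP with placebo. By randomised arm, Months 27 and 36 compare early with delayed MSC-NP. A single coefficient mixes these two questions.

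The coding of treatment after Month 13 is also open. The parallel-group language, and the statement in SAP 1.5 that groups are set at initial randomisation, favour randomised arm. The moving labels in the protocol leave current treatment possible.

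At stake is the adjusted odds ratio, with its interval and p-value, that the SAP commits to report for the primary endpoint. It could appear to contradict a positive Month 13 test even when the Month 13 effect is exactly the one the trial was sized for.

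**Working it through.** **1. What the listed model can estimate.** Write logit P(improved, patient i, visit t) = a_t + b × treatment + covariates + u_i. The log odds ratio for treatment at visit t is (a_t + b + …) − (a_t + …) = b. It is exp(b) at every visit. One odds ratio per visit needs a further term, d_t × treatment.

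**2. Inputs and the plan's own figure.** SAP 1.5 gives 40% versus 5%, 20 per group, and a two-sided pooled Z-test at 0.05. Exact enumeration gives 82.0% power, in line with the stated figure of more than 80% (the normal approximation gives 77.7%). Enrolment is 20/0.8 = 25 per group. The documents give no effect size or power for the mixed model. The Month 13 marginal odds ratio is (0.40/0.60)/(0.05/0.95) = 12.7.

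**3. Timing.** Protocol 6.2 puts the last year 1 dose at Month 10 and the last year 2 dose at Month 24.
- Month 27 is 27 − 10 = 17 months after the early arm's last dose and 27 − 24 = 3 months after the delayed arm's.
- Month 36 is 36 − 10 = 26 and 36 − 24 = 12 months after them.

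**4. Assumed response rates.** Only the Month 13 rates come from the SAP. Months 6 and 20 are left out because the documents give no half-course rate.

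| Scenario | Early arm, Months 13/27/36 | Delayed arm, Months 13/27/36 | Common marginal OR, arm coding |
|---|---|---|---|
| Benefit lasts fully | 0.40/0.40/0.40 | 0.05/0.40/0.40 | 1.71 |
| Lost by the next visit | 0.40/0.05/0.05 | 0.05/0.40/0.05 | 1.00 |
| Half the gain lost at each later visit | 0.40/0.225/0.1375 | 0.05/0.40/0.225 | 1.18 |
| Lasts about 12 months, not 17 | 0.40/0.05/0.05 | 0.05/0.40/0.40 | 0.51 |

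**5. How the common odds ratio arises.** With equal arms, the maximum-likelihood fit of visit + arm matches the observed total at each visit and the observed sum over visits in each arm.
- *Lasts about 12 months, not 17.* Each visit totals 0.45, so the fitted rates are the same at every visit: 0.50/3 = 0.1667 (early) and 0.85/3 = 0.2833 (delayed). OR = (0.1667/0.8333)/(0.2833/0.7167) = 0.51.
- *Lost by the next visit.* Both arms sum to 0.50, so OR = 1.00.
- *Lasts fully.* The arm sums are 1.20 and 0.85. The fitted rates are 0.2715 and 0.1785 at Month 13, and 0.4643 and 0.3357 at each later visit. Check: 0.2715 + 2 × 0.4643 = 1.20; 0.1785 + 2 × 0.3357 = 0.85. OR = (0.4643/0.5357)/(0.3357/0.6643) = 1.71.

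**6. With the random patient effect.** For an assumed random-intercept SD of 1.5, the patient-specific Month 13 odds ratio is 26.4. The common odds ratio is 1.99 (lasts), 1.00 (lost) and 0.49 (12 months, not 17). For SD 0.5 to 3.0 the lasting case gives 1.7 to 2.6, against 13.8 to 131 at Month 13.

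**7. With current-treatment coding.** The common marginal odds ratio is 1.7 to 2.4 if benefit lasts and 8.3 to 12.7 if it is lost. The range depends on whether the delayed arm counts as treated at Month 36.

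**8. Adding the missing term.** When time-by-arm was added in a simulated large sample (SD 1.5, lasting benefit), the estimates were 25.3, 1.05 and 1.02, against true values of 26.4, 1.0 and 1.0.

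**9. Sparse cells.** The chance of no placebo responders at a 5% rate is 0.95^20 = 0.36, or 0.95^25 = 0.28. The ordinary Month 13 odds ratio is then infinite.

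**The case against.** The best defence is that the SAP's intention is clear. It asks for estimates at each time point, tests each year separately and makes year 1 primary. A programmer who delivers that must add the interaction, and the misleading single odds ratio then never appears. This has force: nothing in the SAP shows a preference for a pooled odds ratio, so the figures above describe the model as listed, not a result the trial is bound to report. The conflict still stands. The same section writes out an interaction where it wants one, in the linear model, and lists none with treatment. Unnamed covariates cannot be read as supplying it. Separate fits per visit would leave the stated time effect and random patient effect without a role.

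A reader might infer three stronger claims that the documents do not support.

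- *The primary result or the power is compromised.* They are not: the Month 13 chi-square or Fisher comparison precedes the crossover, is made at that visit alone and does not use this model.
- *The adjusted odds ratio must shrink towards 1.* It may reverse. With current-treatment coding and no carryover it may not be diluted at all. The SAP states neither condition, and Protocol 6.2 plans to look for sustained year 1 effects at Month 27, so absence of carryover cannot be assumed.
- *The linear T25FW and 9HPT model contradicts itself too.* No effect per visit is promised there. Its missing treatment-by-time term is a secondary weakness of specification.

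**Conclusion.** The point holds for the logistic model: as listed, it cannot deliver the estimate the same sentence promises, and the meaning of treatment after Month 13 is undefined. That conclusion is algebraic and needs no assumption.

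The size does rest on assumptions. Against a Month 13 marginal odds ratio of 12.7, the common arm-coded odds ratio is about 1.7, 1.0 or 0.5 under three illustrative courses of benefit. Those later-visit rates, the use of Months 13, 27 and 36 only, and the random-intercept SD are not in the documents, and the three values are not bounds. The defect touches the adjusted and longitudinal estimates only. It should be corrected before the data are analysed, because choosing the model or the coding after seeing results would weaken the adjusted estimate.

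**What to change.** In SAP 4.1:

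- Define treatment as randomised arm at every visit.
- Treat visit as categorical and add arm-by-visit to the logistic mixed model.
- Name the Month 13 arm contrast as the reported adjusted odds ratio. Label it patient-specific, since it need not equal the marginal 12.7.
- Label the Month 27 and Month 36 contrasts as early versus delayed MSC-NP.
- In the linear model for T25FW and 9HPT, add arm-by-visit beside time-by-subtype and report the Month 13 contrast.
- Pre-specify that, if a Month 13 cell has no responders, the reported adjusted odds ratio comes from a separate Month 13 Firth-penalised logistic model with the same covariates. State that this odds ratio is not conditional on a patient effect.

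The cost is SAP wording and model code; no new data are needed. The downside is that visit-specific estimates are less precise than a pooled one.

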9.3 Effectiveness analysis

All statistical analysis will be performed by [name] and her team. Descriptive statistics will be calculated for patients at baseline for the entire cohort

as well as by treatment status. Treatment and placebo group patients will be compared on continuous and discrete baseline characteristics to assess randomization. The EDSS-Plus scale [6] will be used as our primary endpoint with improvement on one or more of the 3 components (EDSS, T25FW and 9HPT). Improvement is defined as ≥ 1 point decrease from baseline EDSS if EDSS at entry is ≤ 5.5 , and a ≥ 0.5 point decrease from baseline EDSS if EDSS at entry is ≥ 6.0 , $\geq 20\%$ positive change in T25FW, and/or $\geq 20\%$ positive change in 9HPT confirmed. The primary endpoint of improvement on one or more of the 3 EDSS-Plus categories between treatment and placebo groups will be assessed bi-varately using the chi-square or Fisher's exact test, as appropriate, at year 1, 2, and 3 of the study. The three components of the EDSS-Plus composite score will also be assessed individually at all time points. A longitudinal linear mixed-effect model will be used to assess longitudinal change (percentage change in mean time) from baseline to 3 years for T25FW and 9HPT, with random intercepts for patients and taking into account treatment status (treatment vs placebo), progression status (SPMS vs PPMS) and time-progression status interaction. Secondary endpoints including 12-item walking scale and urodynamic studies (binary, $\geq 20\%$ improvement in bladder capacity vs $< 20\%$) will also be analyzed. Linear regression models for continuous outcomes and logistic regression models for discrete outcomes will be used to assess the independent effect of treatment status on secondary outcomes, controlling for co-variates. All analyses will be performed in SAS Version 9.4 (SAS Institute Inc., Cary, NC).

Any deviations from the previously described statistical plan will be described and justified in a protocol amendment and/or in the final report submitted to the IND application.

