## 2 VARIABLES FOR ANALYSIS

### 2.1 Analysis of Baseline Data

- Gender (M/F)
- Age at study (years)
- MS subtype (SPMS/PPMS)
- Disease duration (years)
- EDSS score

**Study Name:** Autologous, Bone Marrow-Derived Mesenchymal Stem Cell-Derived Neural Progenitor Cells, Expanded Ex Vivo; Administered Intrathecally (Phase II Trial)

**Principal Investigator:** [name]

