### Secondary Outcomes:

Secondary endpoints including 12-item walking scale and urodynamic studies (binary,  $\geq 20\%$  improvement in bladder capacity vs  $< 20\%$ ) will also be analyzed. Linear regression models for continuous outcomes and logistic regression models for discrete outcomes will be used to assess the independent effect of treatment status on secondary outcomes, controlling for co-variates.

- MSFC → T25FW (time in seconds) + 9HPT (time in seconds) + PASAT (time in seconds)
  - MSFC score =  $\{Z_{\text{arm, average}} + Z_{\text{leg, average}} + Z_{\text{cognitive}}\} / 3.0$
  - reduction in score indicates improvement
- EDSS
  - ranges from 3 to 6.5 for our study (scale ranges from 0 to 10). No units.
  - reduction in score indicates improvement
- T25FW (timed 25-foot walk)
  - time in seconds
  - reduction in time indicates improvement
- 9HPT (9-hole peg test)
  - time in seconds
  - reduction in time indicates improvement
- 12-item MS Walking Scale
  - Total score out of 60, and %
  - reduction in scores or % means improvement
- Urodynamic studies
  - PVR
  - Cystometry with simultaneous measurements of bladder, urethral and subtracted rectal pressures for first sensation
  - Maximum bladder capacity
  - Urethral pressure profile with functional length measurement maximum closing pressure
  - Bladder pressure was assessed with filling and sphincter relaxation and synergic voiding assessed

**Study Name:** Autologous, Bone Marrow-Derived Mesenchymal Stem Cell-Derived Neural Progenitor Cells, Expanded Ex Vivo; Administered Intrathecally (Phase II Trial)

**Principal Investigator:** [name]

- Urinary peak flow rate was also measured.
- 6-Minute Walk Test
  - Distance in meters
  - Increase in distance indicates improvement

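### If the T25FW and 9HPT mixed models use each subject's percentage change in time, the scale is vulnerable to large slowings and, separately, the listed terms omit baseline time.

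*SAP*

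**What the plan says.** Protocol 9.3 and SAP 4.1 (Primary Outcome) both plan a linear mixed model. Protocol 9.3 describes its target as "longitudinal change (percentage change in mean time) from baseline to 3 years for T25FW and 9HPT". The SAP fits it "with random intercepts for patients and taking into account treatment status (treatment vs placebo), disease subtype (SPMS vs PPMS) and time-progression status interaction"; the protocol's list is the same in substance: "taking into account treatment status (treatment vs placebo), progression status (SPMS vs PPMS) and time-progression status interaction". Neither list contains the baseline T25FW or 9HPT time. For this model neither section names a transformation or an analysis that is robust to extreme values.

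Covariates are mentioned in two other places:
- The adjusted odds ratio for the binary composite comes from a "mixed effect logistic regression with fixed effect of time, treatment, relevant covariates, and random effect of patients". That is a different model.
- Under Secondary Outcomes, SAP 4.1 says "Linear regression models for continuous outcomes and logistic regression models for discrete outcomes will be used" and continues "to assess the independent effect of treatment status on secondary outcomes, controlling for co-variates". T25FW and 9HPT appear beneath this in seconds, with the note that "reduction in time indicates improvement". The covariates are not named.

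SAP 2.1 lists gender, age, subtype, disease duration and EDSS as baseline variables, but neither timed test. Both are measured at the baseline visit as parts of the MSFC (Protocol 6.2 and 6.4).

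**The concern.** Two things look wrong, and they are separate.

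**Scale.** A percentage change in a time cannot fall below -100%, but it can rise without limit. In a small arm, one subject who slows sharply can outweigh the improvement of many. By the stratum totals in SAP 1.5, 10 + 2 + 10 + 2 = 24 of the 50 planned subjects enter at EDSS 6.0 or 6.5, and follow-up runs to Month 36, so marked slowing in a few subjects is plausible.

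**Baseline.** If the response is change from baseline, every subject starts at zero, so the random intercept does not stand in for a baseline covariate. Regression to the mean then turns any chance baseline difference between small arms into an apparent difference in change, and available precision goes unused.

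The binary composite discards the size of each change. These models would supply much of the quantitative evidence on two of its three components.

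**Working it through.** **Inputs from the documents.** 20 evaluable subjects per arm and two-sided 0.05 (SAP 1.5). The plan gives no power, SD, correlation or outlier rate for these models. Its one power figure, more than 80% for 40% v 5%, concerns the binary composite; exact enumeration of the pooled Z-test gives 82.0%. Everything below about spread, correlation and outliers is assumed.

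**1. Shift in an arm mean from one subject.** On the percentage scale the shift is x/n. On the log scale the geometric mean moves by exp(ln(1 + x)/n) - 1.

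| Subject's change | Percentage scale, n = 20 | Log scale, n = 20 |
|---|---|---|
| -100% (limit of improvement) | -5 points | not defined |
| +200% | +10 points | +5.6% |
| +500% (10 s to 60 s) | 500/20 = +25 points | exp(ln 6/20) - 1 = +9.4% |

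**2. Effect on a test.** Assume an SD of 20 points, a placebo mean of 0 and a treated mean of -20%. Then t = -20/sqrt(2 × 20²/20) = -3.16. Replace one treated subject by one at +200%:
- The arm mean becomes (19 × (-20) + 200)/20 = -9%, and the arm SD becomes 52.9.
- t = -9/sqrt(52.9²/20 + 20²/20) = -0.71.
- On the log scale (assumed SD 0.20) the ratio is exp((19 ln 0.8 + ln 3)/20) = 0.855, with t = -1.73. The influence is smaller but still present.

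**3. Simulated power at one visit.** 20 per arm, true 18% reduction, assumed log SDs of 0.4 between subjects, 0.15 for change and 0.15 for measurement error, about 4,000 runs per setting (Monte Carlo error under 1 point):

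| Analysis | 5% of subjects slow 3.3-fold | None do |
|---|---|---|
| Percentage change | about 28% | about 65% |
| Percentage change + baseline | about 28% | about 65% |
| Log change | about 41% | about 66% |
| Log change + log baseline | about 41% | about 67% |
| Rank test on percentage change | about 54% | about 63% |

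With outliers, the whole gain comes from the scale.

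**4. Other assumptions.** I took a true 20% reduction, correlations of 0.6 to 0.9 and log SDs of 0.3 to 0.7. Moving from percentage change to log change with log baseline gains 0 to 9 points without outliers. It gains about 7 to 26 points if 5% of subjects slow threefold. A baseline term alone on the percentage scale adds 0 to 8 points without outliers and -1 to +2 with them.

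**5. Precision from the baseline term.** With equal variances at baseline and follow-up, the variance ratio of adjusted analysis to change score is (1 + ρ)/2. The standard error therefore falls by 1 - sqrt((1 + ρ)/2):
- ρ = 0.9: 1 - sqrt(0.95) = 2.5%
- ρ = 0.8: 1 - sqrt(0.90) = 5.1%
- ρ = 0.6: 1 - sqrt(0.80) = 10.6%

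**The case against.** **The sentence is loose.** It can be read as a model of repeated times, baseline included, with the result summarised as a percentage change in group means. On that reading baseline is already in the model. The term list also looks incomplete, since it names a time interaction but no main effect of time. This stands: the two weaknesses are conditional on the subject-level reading. It also shows that the response needs defining.

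**These are not the only continuous analyses of the two tests.** SAP 4.1 lists both in seconds under generic linear regression with covariates, and the MSFC combines them. This also stands. Because those covariates are unnamed, that text neither excludes the baseline value nor prespecifies it.

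**The magnitude rests on assumed inputs.** No document gives a 5% rate of 3.3-fold slowing. Entry requires stable disease, and stratification by EDSS limits some imbalance. Without outliers the gain is about 2 points in the main setting. All of this is fair. The simulation also covers a single visit, and a single bad visit would be diluted in the repeated-measures model. Persistent slowing would not be: averaged over four visits, power was 31% on percentage change v 47% on log time with baseline.

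**Log time is not the best remedy for outliers.** The rank test did better in the outlier setting (about 54% v 41%). This stands, and is why the fix includes one.

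**Random noise does not bias the comparison.** A reader might infer bias because noise with log SD 0.3 gives a mean apparent slowing of exp(0.3²/2) - 1 = 4.6%. It arises in both arms and cancels; with no true effect and no outliers, the simulated difference between arms was -0.01 points.

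**Conclusion.** The point holds as two separate, conditional weaknesses in supportive analyses. If the response is each subject's percentage change, the scale lets one large slowing dominate a 20-subject arm: 25 points for +500%, and about 28% v 41% power under the assumed outlier rate. Where there are no such subjects, little is lost (about 65% v 67%). The missing baseline term costs a modest amount of precision, about 2.5% to 11% of the standard error for assumed correlations of 0.9 to 0.6, and leaves chance imbalance unadjusted.

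A reader might infer two stronger conclusions that the documents do not support:
- *The missing baseline term is what lets one subject swamp an arm.* It is not. Adding it on the percentage scale leaves power at about 28%.
- *The trial's main result is at risk.* The primary test is the binary composite at Month 13, where an extreme slowing counts at most as one non-improvement.

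**What to change.** In SAP 4.1 and Protocol 9.3:
- Define the response as log(time) at each post-baseline visit.
- Add log baseline time of the same test, and for 9HPT of the same hand, to the terms already listed.
- Report the back-transformed treatment ratio as a percentage difference.
- Add a rank-based sensitivity analysis, because the log scale reduces outlier influence but does not remove it.

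In the linear regressions under Secondary Outcomes in SAP 4.1, name the baseline value of the same outcome as a covariate. Keep the 20% responder analyses unchanged.

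The cost is wording in both documents, one changed model statement and one added sensitivity analysis. No new data are needed, since the baseline times are already collected. The change should be made before the data are analysed.
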